8.6. Subject Withdrawal Criteria

Subjects will be informed that they have the right to withdraw from the study at any time for any reason, without prejudice to their medical care. Study drug must be permanently discontinued

and the subject withdrawn from the study for any of the following TEAEs, with the subject managed as indicated:

- **Palmar-plantar Erythrodysesthesia (PPE):** For mild to moderate symptoms of PPE (e.g., redness, pain, or scaling of hands or feet), study drug should be interrupted and symptomatic measures, including hand cream such as “Udder Cream”, instituted immediately. Study drug may be resumed after resolution of symptoms. Study drug should be permanently discontinued at the first sign of significant/severe, redness, pain, or scaling of hands or feet, and symptomatic measures instituted immediately.
- **Dyspnea or suspected pneumonitis:** Study drug should be permanently discontinued for subjects with shortness of breath or other respiratory symptoms that are otherwise unexplained. The subject is to be carefully monitored for improvement. In the event that symptoms worsen or present as more than mild intensity, immediate referral to a qualified pulmonologist for definitive diagnosis and treatment should be undertaken.
- **Visual symptoms (including keratitis):** Study drug should be permanently discontinued at the first sign of significant, redness, pain, or dryness of the eyes. Symptomatic measures, including moisturizing eye drops should be instituted. In the event that symptoms worsen or present as more than mild, immediate referral to a qualified ophthalmologist should be undertaken.
- **Evidence of drug-induced liver injury (DILI);** Study drug should be permanently discontinued for subjects with evidence of DILI; see [Appendix A](#) for details.

Refer to the Study Manual for additional details regarding the assessment and management of these events.

Furthermore, the Investigator also has the right to withdraw subjects from the study for any of the following reasons:

- Progression of underlying disease that, in the opinion of the Investigator, precludes further study treatment.
- Occurrence of any other unacceptable AE.
- Study drug interruption for any reason for >7 days.
- Subject requires use of a prohibited concomitant medication or therapy.
- General or specific changes in the subject’s condition unacceptable for further treatment within the study parameters, in the judgment of the Investigator.
- Non-compliance.

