8.9. Subject Adherence to Protocol Schedule

All subjects are required to adhere to the protocol-specified visit schedule.

Subjects will be evaluated for study eligibility during the screening period, within 60 days before randomization. All subjects must provide written informed consent before any study-related samples are collected or evaluations performed in this study.

Subjects who are determined to be eligible for the study will be randomized within 24 hours before baseline (Day 1, the first day of study drug administration). Thereafter, subjects are to attend study center visits at Day 2 and Week 2, 4, 8, and 12. Subjects who discontinue study drug before completion of the Week 12 visit are to attend an Early Termination visit within 1 week after the last study drug dose. All study visits are to be conducted on an out-patient basis. Additional study center visits may be scheduled, as deemed necessary based on the subject's clinical status.

Permissible visit windows are specified in [Table 2](#).

A Follow-up visit will be conducted at Week 16 (± 1 week) for MRI-PDFF, measurement of liver aminotransferases, and safety assessments. Additional safety follow-up may be required thereafter if drug-related AEs have not resolved at that time.

Failure to attend scheduled study visits within the protocol-specified windows may result in discontinuation from the study.

The Sponsor notes that the COVID-19 pandemic may impact the conduct of the 50 mg and 75 mg cohorts, with challenges potentially arising from quarantines and travel limitations affecting study subjects as well as clinic and imaging facility closures. Accordingly, safety assessments scheduled for the Week 12 and 16 visits, as identified in [Table 2](#), including sample

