8.1.2. Protocol Deviations

Protocol deviations will be identified and classified as important or not important. Important protocol deviations may include but are not limited to:

- Violation of Inclusion/Exclusion Criteria
- Study drug compliance $\leq 80\%$ or $\geq 120\%$
- Use of prohibited therapies
- Incorrect treatment

Important protocol deviations deemed to possibly affect the efficacy measurements or integrity of any other key study data may be identified prior to database lock to support defining the PP population.

Sponsor: Sagimet Biosciences
Protocol Number: 3V2640-CLIN-005
Version and Date: Final Version 1, 02June2020

Protocol deviations including category will be summarized by treatment group and overall for the study. Protocol deviations due to COVID impact will be identified as such.

A listing of protocol deviations will be provided.

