8.2. Study Drug Exposure and Compliance

Duration of drug exposure will be summarized both as a continuous and a categorical variable for the safety population. Exposure will be calculated as:

$$\text{study drug stop date} - \text{study drug start date} + 1 \text{ [converted to weeks (days divided by 7)]}$$

Categories for reporting exposure will include < 2 weeks; 2 weeks - <4 weeks; 4 weeks - <8 weeks; 8 weeks - <12 weeks; \geq 12 weeks.

Drug accountability is captured in the eCRF at each visit. The eCRF captures the number of pills dispensed, the number returned, and the number missed during the dosing period. Overall compliance will be determined based on pill counts over each visit period and taking into account the number missed. Compliance will be derived as:

$$\frac{[(\text{# of pills dispensed} - \text{# of pills returned}) - \text{# of missed pills}]}{\text{number of days within the visit period}} \times 100$$

Where number of days within the visit period is derived as:

$$\text{Date of Visit (X+1)} - \text{Date of Visit (X)} + 1$$

Compliance will also be summarized for the following categories < 80%, 80% - 120%, and > 120%.

Mean daily dose (mg) and total cumulative dose (mg) received will also be summarized. Total cumulative dose will be summarized overall and separately for those that had extended dosing.

Listings of planned and actual treatments, overall compliance, and drug exposure will be produced.

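### SAP 8.2 counts days after the last dose, and days of protocol-directed interruption, as days on which a dose was due, so compliance is understated for some adherent subjects (minor)

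*SAP*

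**What the plan says.** SAP 8.2 sets out the data and the rule. "The eCRF captures the number of pills dispensed, the number returned, and the number missed during the dosing period". From these, "Overall compliance will be determined based on pill counts over each visit period and taking into account the number missed". The numerator is tablets dispensed less tablets returned, less tablets missed. The denominator is the date of the next visit minus the date of the current visit, plus 1. It has no cut-off at the last dose and no term for interruption. The same section computes exposure from the study drug start and stop dates.

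The protocol creates days on which no dose is due:

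- Protocol 8.9: subjects who stop drug before completing the Week 12 visit "are to attend an Early Termination visit within 1 week after the last study drug dose".
- Protocol 8.6: for mild to moderate palmar-plantar erythrodysesthesia (PPE), drug is to be interrupted, and "Study drug may be resumed after resolution of symptoms".
- Protocol Appendix A: drug is to be interrupted for certain liver-test elevations.

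The result is used in three places. SAP 8.2 tabulates compliance below 80%, 80% to 120%, and above 120%. SAP 8.1.2 gives compliance at or below 80%, or at or above 120%, as an example of an important deviation, and summarizes deviations by treatment group. It adds: "Important protocol deviations deemed to possibly affect the efficacy measurements or integrity of any other key study data may be identified prior to database lock", in support of a per-protocol (PP) population. SAP 5 says that a PP population may be defined, for sensitivity analyses, from within the mITT.

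**The concern.** A compliance percentage is normally read as doses taken out of doses due. Here a subject who follows every instruction, including an instruction to stop or interrupt drug, is scored as if doses had been skipped. The SAP does not say that this is intended, and it leaves exposure and compliance on different time bases for anyone who stops early.

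At stake is the accuracy of two descriptive tables and of one input to the PP decision. Protocol 5.1 names skin and eye effects as the principal toxicities of the drug, so interruptions and early stops may be more frequent on active treatment, and the understatement may then differ by arm. PP membership is a judgement, and Protocol 9.9 leaves study personnel other than imaging staff unblinded. The compliance figure behind that judgement should therefore be correct and fixed in advance.

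**Working it through.** The plan states no compliance result, so there is no figure of its own to reproduce. The SAP 8.2 rule is applied to fully adherent subjects.

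**Inputs**
- One tablet daily on placebo, 25 mg and 50 mg (Protocol 9.5).
- Early Termination visit 0 to 7 days after the last dose (Protocol 8.9).
- mITT: at least 8 weeks of drug, 56 days (SAP 5). This is taken as the span from first to last dose, as SAP 8.2 measures exposure.
- Deviation example: compliance at or below 80% (SAP 8.1.2).
- Assumptions: one pooled ratio over the whole treatment period (the SAP does not say how the visit periods combine); accountability visits on Days 1, 15, 29, 57 and 85.

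Steps 1 to 3 set aside the +1 and the missed-pill term, to isolate this mechanism. For stops, each calendar day from Day 1 through the Early Termination visit is counted once. For completers, the 84 treatment days are counted.

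**1. Permanent stop on Day n, visit 7 days later: n/(n+7)**

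| Last dose | Calculation | Score |
|---|---|---|
| Day 14 | 14/21 | 66.7% |
| Day 28 | 28/35 | 80.0% |
| Day 42 | 42/49 | 85.7% |
| Day 56 | 56/63 | 88.9% |
| Day 63 | 63/70 | 90.0% |
| Day 70 | 70/77 | 90.9% |

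A score of 80% or less needs n of 28 or less. A shortfall of 10 points or more needs n of 63 or less. At a 3-day lag the Day 56 score is 56/59 = 94.9%; at zero lag it is 100%. If the visit day itself is not counted, the denominator is n+6: 28/34 = 82.4% and 56/62 = 90.3%.

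**2. Completer with k days of directed interruption: (84 - k)/84**
- k = 7: 77/84 = 91.7%.
- k = 9: 75/84 = 89.3%, the first shortfall of 10 points or more.
- k = 14: 70/84 = 83.3%.
- k = 17: 67/84 = 79.8%, the first score at or below 80%.

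**3. Both together: 56-day span, 7 days interrupted, lag L: 49/(56 + L)**
- L = 5: 49/61 = 80.3%.
- L = 6: 49/62 = 79.0%.
- L = 7: 49/63 = 77.8%.

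So this case crosses 80% only at a lag of 6 or 7 days. With a 7-day lag and a 7-day interruption, a stop on Day 63 gives 56/70 = 80.0% and a stop on Day 70 gives 63/77 = 81.8%.

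**4. The +1 put back, once per visit period**
- Completer denominator: 15 + 15 + 29 + 29 = 88. With no interruption, 84/88 = 95.5%; that 4.5-point loss comes from the +1 alone and is a separate matter. With 7 days interrupted, 77/88 = 87.5%; with 14 days, 70/88 = 79.5%.
- Stop on Day 56, visit on Day 63: 15 + 15 + 29 + 7 = 66. Stop alone, 56/66 = 84.8%, the lowest stop-only score within mITT. With a 7-day interruption, 49/66 = 74.2%.
- A stop alone reaches 80% or less only up to Day 36: 36/(15 + 15 + 15) = 80.0%.

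**5. After the change proposed below**
- Stop on Day 56: 56/56 = 100%.
- Completer with a 7-day directed interruption: the main figure stays at 91.7% (+1 set aside), and the additional figure is 77/77 = 100%.

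**The case against.** A reader might infer more than the documents support, in three ways.

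- **That adherent subjects in general score 10 points or more too low.** They do not. Without a stop or an interruption this mechanism costs nothing. A 7-day interruption costs 8.3 points. For stops, 10 points needs both a stop by Day 63 and the full 7-day lag, which is the upper limit of the window rather than a typical value.
- **That early stopping pushes subjects out of the PP set.** PP is drawn from mITT. The 66.7% and 80.0% scores belong to subjects with less than 8 weeks of drug, who are already outside both. Within mITT a stop alone does not reach 80%. Nor is exclusion mechanical: the PP population is optional, low compliance is listed only as a possible important deviation, and exclusion takes a judgement that the data may be affected.
- **That the efficacy conclusion is at risk.** The primary and key secondary analyses use mITT, where this compliance percentage plays no part.

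Three further points stand. Scoring interrupted days as untaken drug can be defended as a measure of dose received against the planned daily schedule. Long interruptions should be unusual, because Protocol 8.6 lists more than 7 days as a discretionary reason for withdrawal. Frequency and imbalance between arms cannot be estimated: PPE occurred in 2 of 12 subjects with metabolic syndrome at 50 to 150 mg (Protocol 5.1), but none of the 6 given 50 mg had a treatment-emergent event (Protocol 9.7).

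None of this justifies counting days after a permanent stop. No dose is due then, and the SAP already uses the stop date for exposure.

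**Conclusion.** The point holds, as a minor one. The denominator in SAP 8.2 runs past the last dose and through directed interruptions, and so understates compliance for some subjects who did what they were told. The size depends on the lag, the stop day and the length of interruption. Within mITT, a score at or below 80% requires a stop combined with an interruption, or a long interruption of about 17 days (about 14 with the +1).

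The consequence is confined to the compliance categories, the deviation summary and, by judgement, an optional PP sensitivity set. This rests on pooled counts, nominal visit days, one tablet a day, and reading the 8-week mITT requirement as the span from first to last dose. If it means 56 days of actual dosing, the 49-tablet example in step 3 falls outside mITT.

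**What to change.** In SAP 8.2:

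1. End the denominator of the last period at the earlier of the next visit and the last-dose date.
2. Where interruption dates are recorded, also report compliance with directed interruption days left out, and report the number of interruption days separately. Keep this as an additional figure, since removing those days from the main one is a definitional choice.

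In SAP 8.1.2, state that a subject is not classified as an important compliance deviation solely because of directed interruption days.

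The cost is a few lines of SAP wording and minor programming. The first change needs only the stop date. The rest depends on interruption dates and reasons being recorded. The accountability items named in SAP 8.2 do not include them, and the planned listing of dosing adjustments (16.2.5.3) appears in the Cohort 3 addendum, so availability for Cohorts 1 and 2 should be confirmed first.

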8.3. Efficacy

8.3.1. Primary Efficacy Endpoint and Analyses

The primary efficacy endpoint is the percent change from baseline in liver fat at Week 12, as determined by MRI-PDFF. In the primary analysis, missing Week 12 values for MRI-PDFF will be imputed with the last post-baseline observation on or after Week 8 in the mITT (i.e., last observation carried forward [LOCF]).

8.3.1.1. Primary Analysis of the Primary Efficacy Endpoint

The initial analysis of the primary efficacy endpoint will be performed using an ANCOVA model with fixed effects for the stratification factor (diabetes presence/absence), and treatment group (TVB-2640 50 mg and pooled placebo) with the baseline MRI-PDFF value as a covariate including all subjects in the mITT from the US.

Sponsor: Sagimet Biosciences
Protocol Number: 3V2640-CLIN-005
Version and Date: Final Version 1, 02June2020

The primary efficacy analyses will be based on a F-test from the ANCOVA model in the mITT to compare each TVB-2640 dose group individually with the placebo group. Data normality will be assessed and the appropriate data transformation will be applied to fulfill the underlying assumption of the ANCOVA model. Model residuals will be calculated and plotted to visually inspect the model assumptions of homoscedasticity and normality for the primary efficacy analysis. If, upon visual inspection, the model assumptions of homoscedasticity or normality are not met, then the primary efficacy analysis will be repeated after making an appropriate transformation (e.g., log transformation) of the data. If a suitable transformation cannot be determined the corresponding rank ANCOVA will become the primary analysis for this endpoint.

The equal slopes assumption for the primary analysis will be assessed by including a term for the treatment by baseline MRI-PDFF interaction. If the equal slope assumption is not met (p-value for interaction less than 0.05), then the primary analysis will be repeated with the interaction term included in the model and the LS Means and treatment difference in the LS Means will be tested and summarized at the 25th, 50th, and 75th percentile for the baseline MRI-PDFF. This analysis will be considered secondary and supportive of the primary analysis.

Summary statistics will be displayed by treatment group along with the difference in least squares means (and the associated 95% confidence interval and p-value) for each TVB-2640 dose group to pooled placebo comparison. If data is transformed for analysis, then LS means will be back transformed to the original scale where appropriate.

The fixed-sequence method, as described in Section 7.3, will be used to maintain an overall 0.05 Type I error rate for the final analysis.

In the primary analysis, missing Week 12 values for MRI-PDFF will be imputed with the last post-baseline observation on or after Week 8 in the mITT.

Subjects who required extended dosing beyond 12 weeks will be excluded from the primary efficacy analysis. See Appendix 1 for additional details on COVID-19 impacts and data handling considerations.

The primary analysis will be based on the mITT population.

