3.5. Timing of Analyses

An interim analysis for SRC review will be performed after all of the subjects in the 25 mg dose level complete the 12-week treatment period. Details on data requirements and outputs required will be maintained in the SRC Plan or other related documents.

An additional SRC analysis was performed during the COVID pandemic to confirm safety prior to allowing the option for extended 50 mg cohort dosing.

The primary analysis of efficacy will be performed when all subjects in the US 50 mg cohort finish their final visit. The primary analysis will not include any data from China, due to delays and uncertainty of enrollment in the Chinese cohort.

An End of Study final analysis will be performed when the final subject completes the study and will include cumulative data from the US and China as applicable.

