7.1. Stratification and Covariates

At each dose level, subjects will be randomly assigned to TVB-2640 or placebo at a 2:1 ratio, with randomization stratified by type 2 diabetes mellitus status (present/absent). The 50 mg dose level will also be stratified by country (US/China) for the final analysis. Selected statistical models and tests will be stratified based on the randomization strata. Details on the models and tests are provided in the relevant sections below.

This is a multi-center trial. However, adjustment for study center will not be made in the statistical tests.

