7.3. Multiple Comparisons and Multiplicity

In order to control for multiple comparisons, the primary and key secondary efficacy analyses will be tested using a fixed-sequence strategy to maintain the overall Type I error rate at 0.05. Each test in the fixed-sequence, uses a 2-sided test at the 0.05 level of significance and starts with the primary efficacy analyses. The first comparison to be assessed for significance is the primary efficacy endpoint analysis of the high-dose group (50 mg TVB-2640) compared to placebo and if statistically significant, testing will proceed to the low-dose group (25 mg TVB-2640) comparison. If both comparisons of the primary efficacy endpoint are significant, then testing will proceed to the key secondary efficacy endpoint. The key secondary efficacy analyses will be tested in a similar fashion, first comparing the high dose group (50 mg TVB-2640) with placebo and if statistically significant, testing will proceed to the low dose group (25 mg TVB-2640) comparison.

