8.3.1.2. Additional Analyses of the Primary Efficacy Endpoint

The primary efficacy analysis will be repeated using the ITT population, ATP, and PP population. Analyses will be conducted with LOCF from Week 8 onward and repeated excluding missing data (no LOCF).

In addition to the primary analysis of Week 12 that includes all subjects who had no more than 12 weeks of study treatment, an analysis of the End of Treatment MRI-PDFF data including data from the extended dosing subjects will be performed in the mITT, ITT, ATP, and PP populations.

An analysis of MRI-PDFF data in the log scale will be performed in the mITT population. The log ratio of Week 12 to baseline [$\log(\text{Week 12}/\text{Baseline})$] will be analyzed using a similar

ANCOVA mode. In the event that model assumptions are not met for the primary efficacy analysis noted above, the analysis in the log scale will become primary.

At the time of the final analysis, the above analyses will be repeated using all data from the US and China. Subset analyses will be performed on the primary efficacy endpoints for subjects enrolled in US and China to evaluate the consistency of results between subjects enrolled in each country. The ANCOVA model will incorporate fixed effects for the stratification factor (diabetes presence/absence), country (US/China), treatment group (TVB-2640 50 mg and pooled placebo), and country-by-treatment interaction and with the baseline MRI-PDFF value as a covariate including all subjects in the mITT from US and China who received 50 mg or placebo.

A test for country-by-treatment interaction will be performed. If there is no interaction detected ($p \geq 0.05$), the primary efficacy endpoint, percent change from baseline in hepatic fat fraction at Week 12, as determined by MRI PDFF, will be analyzed using an ANCOVA model with fixed effects for the stratification factor (diabetes presence/absence) and treatment group (i.e., TVB-2640 dose groups and pooled placebo) and with the baseline MRI-PDFF value as a covariate including all subjects from US and China (with no fixed effect for country). If the country-by-treatment interaction is significant ($p < 0.05$) then a separate analysis will be performed on subjects enrolled in China in the 50 mg cohort. This analysis is not powered to detect a significant difference but would be supportive/descriptive in nature to evaluate trends.

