9. CHANGES TO THE PLANNED ANALYSES

The timing of the primary efficacy analysis will be based on completion of the US 50 mg cohort. The protocol indicated the initial analysis of the primary efficacy endpoint would be performed using subjects from US and China and include country as an effect in the ANCOVA model. Given the delays in enrollment in China due to COVID-19, the primary analysis has been adjusted to only include the US cohorts and a modified ANCOVA model as described above.

The treatment group used for the presentation of data based on the mITT population has been modified from the protocol. Per the study protocol, the data were to be analyzed based on randomized treatment.

As a point of clarification and as noted for the key secondary efficacy analysis above, due to data collection precision, subjects with a reduction of at least 29.5% from baseline will count as responders. Similar conventions were used for the sensitivity analyses of that endpoint using different responder definitions.

Since one subject received the incorrect study treatment (active instead of placebo), an as-treated population (ATP) has been added to the SAP. The ATP will be used to evaluate the treatment differences in efficacy endpoints using treatment received instead of randomized treatment.

Due to the impact of COVID-19, all efficacy endpoints will be analyzed at End of Treatment and End of Study. The definition of those timepoints are described in section 3.1. Per the protocol, endpoints were evaluated at Week 12 and Week 16 but the differences in duration of treatment require further evaluation given the visits may not correspond to the number of weeks specified in the protocol visit schedule.

An additional SRC analysis was performed during the COVID-19 pandemic to confirm safety prior to allowing the option of extended 50mg cohort dosing. If additional SRC reviews are performed, they will be discussed in the CSR.

Additional supplementary and sensitivity analyses related to the protocol-planned analyses have been added to the SAP. Specifically, the absolute change from baseline in MRI-PDFF has been added in addition to the planned percent change. The change from Week 12 to Week 16 in MRI-PDFF has been added. ALT and AST normalization has been added as an additional analysis of the liver aminotransferases.

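### SAP 8.3.1.1 assigns the fixed sequence and overall 0.05 to the final (US+China) analysis, although SAP 3.5 and 9 make the US-only analysis primary; a lesser point is that the pooled model omits country

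*SAP*

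**What the plan says.** **Which analysis is primary.** SAP 3.5: "The primary analysis will not include any data from China, due to delays and uncertainty of enrollment in the Chinese cohort". SAP 9 repeats it as a declared change: "the primary analysis has been adjusted to only include the US cohorts and a modified ANCOVA model as described above".

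**What the final analysis is.** SAP 3.5: "An End of Study final analysis will be performed when the final subject completes the study and will include cumulative data from the US", together with China as applicable. SAP 7.1: "The 50 mg dose level will also be stratified by country (US/China) for the final analysis". SAP 8.3.1.2: "At the time of the final analysis, the above analyses will be repeated using all data from the US and China". SAP 8.3.2 uses the term in the same way for the secondary endpoints.

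**Where alpha is placed.** SAP 7.3 says that "the primary and key secondary efficacy analyses will be tested using a fixed-sequence strategy to maintain the overall Type I error rate at 0.05", without naming a data cut. SAP 8.3.1.1, headed as the primary analysis and fitted to US mITT subjects, closes with "The fixed-sequence method, as described in Section 7.3, will be used to maintain an overall 0.05 Type I error rate for the final analysis".

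**Interaction rule.** In SAP 8.3.1.2, if the country-by-treatment p-value is 0.05 or more, the endpoint is refitted on US and China together with no country effect. If it is below 0.05, "then a separate analysis will be performed on subjects enrolled in China in the 50 mg cohort". Only that China analysis is called supportive; the US+China repeat is not. Protocol 13.2.2 differs: the interaction test selects the primary population, which is both countries if p is 0.05 or more and the US alone otherwise.

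**The concern.** Every later step of the sequence (25 mg on the primary endpoint, then both doses on the key secondary) depends on the 50 mg result. SAP 3.5 and 9 point to the US-only test as the one that opens the sequence. Taken at its word, the alpha sentence in 8.3.1.1 points to the US+China test. The US result is available first, so if the wording stays open, the choice could be made with both results in hand.

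The lesser point concerns the pooled model. The 50 mg cohort is randomised by country and the 25 mg cohort has no China subjects. A model without country therefore lets any overall difference between the countries enter both dose comparisons. The US-only analysis is unaffected.

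**Working it through.** **Inputs.** SD 30, difference 24, and 30 evaluable US subjects per group (SAP 3.3). China 18 active and 9 placebo, all in the 50 mg cohort (SAP 3.2). Pooled totals: 50 mg 30+18 = 48; placebo 30+9 = 39; 25 mg 30.

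**The plan's own power first.** Simulated two-sided Wilcoxon tests on lognormal data with SD 30, placing the placebo Week 12 value at 100% of baseline (an assumption; the SAP gives no location), give 83% power for both doses, or 80% under a pure location shift. The plan says at least 80%. For 30 v 15 the result is 76.9%, against 77% stated. The stated figures stand.

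**Overlap of the two 50 mg tests.** They share 60 of 87 planned subjects. Information is 1/(1/30+1/30) = 15.0 for US-only and 1/(1/48+1/39) = 21.5 pooled, so the correlation is sqrt(15.0/21.5) = 0.835.

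**Simulation.** Three-arm t-tests without covariates, two-sided 0.05, planned numbers. The interaction test in 50 mg and placebo subjects has SE 30 x sqrt(1/30+1/30+1/18+1/9) = 14.49.

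Type I error, 50 mg v placebo:

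| Rule | Error |
|---|---|
| US-only as sole test | 5.0% |
| Pooled as sole test | 5.0% |
| Protocol 13.2.2 gated rule | 5.8% |
| Claim on either result | about 7.5% |

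Trials in which the pooled model is run (interaction p at least 0.05) and disagrees with US-only:

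| Effect US / China | Disagree | Pooled only significant | US only significant |
|---|---|---|---|
| 24 / 24 | 9.1% | 8.6% | 0.5% |
| 24 / 0 | 13.4% | 0.7% | 12.7% |

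Power for 50 mg at 24 points in the US is 86.5% for US-only. For the gated rule it is 94.6% if China has the same effect, about 86% if China has 12 points, and 74.5% if China has none.

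**Country term.** China shares are 0/30 (25 mg), 18/48 = 0.375 (50 mg) and 9/39 = 0.231 (placebo). With a China-minus-US shift of X points, the contrasts without a country term move by:
- 25 mg v placebo: 0 - 0.231 = -0.23X
- 50 mg v placebo: 0.375 - 0.231 = +0.14X

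X is not in the documents. For an assumed X of 5 to 15 points the shifts are -1.2 to -3.5 and +0.7 to +2.2 points. From the design matrix, adding country raises the SE from 6.47 to 6.55 for 50 mg (6.547/6.467 = 1.012) and from 7.29 to 7.46 for 25 mg (7.464/7.285 = 1.025).

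**The case against.** The best defence is that the intent is clear. SAP 7.3 applies the sequence to the primary and key secondary analyses, SAP 3.5 and 9 define the primary analysis as US-only, and the US+China repeat sits under additional analyses. Choosing the pooled result afterwards would go against 3.5 and 9. This stands as evidence of intent, and it is why a wording change is enough. It does not remove the contradiction, because the sentence that allocates alpha names the other analysis.

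Much of the disagreement at 24/24 is simply the pooled test gaining power from 27 more subjects. That is also true, but the 24/0 case runs the other way, so the choice matters in both directions.

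Three stronger readings are tempting and are not supported:
- A reader might infer that type I error is inflated. About 7.5% arises only if either result may be claimed, and no passage says so.
- A reader might infer that a significant interaction leaves no 50 mg test. SAP 7.2 runs all analyses by country as well as overall, and 8.3.1.1 already specifies the US test. What is missing in 8.3.1.2 is a statement of which test then carries the sequence.
- A reader might treat Protocol 13.2.2 as superseded by SAP 9. SAP version 1 rests on protocol 6.0 and lacks Cohort 3; the SAP addendum ties Cohort 3 to protocol 7.0 of March 2021. The supplied protocol contains Cohort 3, so it appears to postdate SAP version 1, and it keeps the interaction-gated rule.

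On country, the omission follows the protocol and touches only the pooled model, and X is unknown. That makes it the lesser point.

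**Conclusion.** The alpha sentence in SAP 8.3.1.1 is wrong as written and should be fixed. It conflicts with SAP 3.5 and 9, and the protocol and SAP disagree on whether the interaction test selects the primary population, so the two must be reconciled. This is a contradictory allocation of alpha. It is not a demonstrated loss of error control, and no stated power or sample-size figure is wrong.

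The size is a disagreement between the two candidate 50 mg tests in roughly 9% to 13% of trials over the two scenarios tabulated. This rests on planned numbers, SD 30, the full China cohort and models without baseline or diabetes adjustment. It falls to zero if China contributes no data, which SAP 3.5 allows for.

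Omitting country is a modest, avoidable confounding of both dose contrasts in the pooled model. Its size depends on X.

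**What to change.** **Fix 1, needed.**
- In SAP 8.3.1.1, replace *for the final analysis* with *for the US-only mITT primary analysis (Section 3.5)*, and state the same population in SAP 7.3.
- In SAP 8.3.1.2 and 8.3.2, label the End of Study US+China analyses supportive, with nominal p-values.
- At the next amendment, align Protocol 13.2.2 so that the interaction test no longer selects the primary population.

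The cost is wording in the SAP and one item in a protocol amendment, which needs IRB re-approval under Protocol 14.2; hence the timing. The statistical price is that pooled data support no formal claim: 50 mg power is 86.5% US-only, against 94.6% for the gated rule if China has the same effect.

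**Fix 2, a cheap improvement.** Keep country as a fixed effect in the pooled ANCOVA. The cost is one model term and an SE that is 1.2% larger for 50 mg and 2.5% larger for 25 mg.
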